7.1.5.1.2 Visit 2: Baseline

Patients will be randomized to either treatment or sham stimulation and assigned a code. Before starting stimulation, the researcher will conduct a vital signs and neurological examination. Then, the patient will be subjected to the first tSCS stimulations (a 30 min stimulations).

7.1.5.1.3 Visit 3-5: Stimulation Visits

At each visit the patient will be reassessed for vital signs. After the completion of each session period. 9HPT will be assessed the last day of stimulation for each session period.

7.1.5.1.2 Visit 13, 14 and 29: end of DBP, onset and end of OLE

During such visits, vital signs, and neurological exam and 9HPT will be conducted.

7.2 Assessing and Recording Adverse Events

An adverse event is defined as any untoward medical occurrence in a clinical investigation subject administered a medical device treatment and which does not necessarily have to have a causal relationship with this treatment. An adverse event can therefore be any unfavorable and unintended sign (including an abnormal laboratory finding, for example), symptom, or disease temporally associated with the use of a medicinal product or protocol specified procedure, whether considered related to the medicinal product or protocol specified procedure. Any worsening (i.e., any clinically significant adverse change in frequency and/or intensity) of a preexisting condition that is temporally associated with the use of the product, is also an adverse event.

Changes resulting from normal growth and development that do not vary significantly in frequency or severity from expected levels are not to be considered adverse events.

Examples of this may include, but are not limited to, teething, typical crying in infants and children and onset of menses or menopause occurring at a physiologically appropriate time.

Product includes any device, diagnostic agent, pharmaceutical product, biological product, or protocol-specified procedure, whether investigational (including sham or active comparator treatment) or marketed, manufactured by, licensed by, provided by, or distributed by the vendor for human use.

Adverse events may occur during clinical trials, or as prescribed in clinical practice, from inadequate therapeutic regimen (whether accidental or intentional), from abuse and from withdrawal.

Electronic reporting procedures can be found in the electronic data capture (EDC) entry guidelines. Paper reporting procedures can be found in the Investigator Trial File Binder (or equivalent).

7.2.1 Definition of an Over-treatment for this Protocol and Reporting of Over-treatment

In this trial, an over-treatment is any therapeutic regimen of higher intensity or of longer duration than the specified therapeutic regimen to be administered in a calendar day (accidental or intentional). If an adverse event(s) is associated with (“results from”) the over-treatment, the adverse event(s) is reported as a serious adverse event, even if no other seriousness criteria are met. If the therapeutic regimen meeting the protocol definition of over-treatment is taken without any associated clinical symptoms or abnormal laboratory results, the over-treatment is reported as a non-serious Event of Clinical Interest (ECI), using the terminology “accidental or intentional over-treatment without adverse effect.”

All reports of over-treatment with and without an adverse event must be reported by the investigator within 24 hours either by electronic media or paper. Electronic reporting procedures can be found in the electronic data capturing (EDC) entry guidelines. Paper reporting procedures can be found in the Investigator Trial File Binder (or equivalent).

7.2.2 Reporting of Pregnancy and Lactation

Female participants may screen for this study if:

- They are surgically sterile [have had a hysterectomy (uterus removed), bilateral oophorectomy (ovaries removed), or tubal ligation at least 6 months prior]
- They are of post-menopausal age and have not had a menstrual period for 12 months
- They have a vasectomized partner (performed at least 6 months prior) who has been documented to no longer produce sperm
- They are using a highly effective method of contraception to avoid pregnancy throughout the study and for 30 days after you complete this study.

Examples of acceptable forms of highly effective contraception include:

1. Established use of oral, injected or implanted hormonal methods of contraception plus use of a condom for your male partner.
2. Placement of an intrauterine device (IUD) or intrauterine system (IUS) plus use of a condom for your male partner.
3. True abstinence: When this is in line with your preferred and usual lifestyle

NOTE: Periodic abstinence (e.g., calendar, ovulation, symptothermal, post ovulation methods), condoms alone or double barrier are not acceptable methods of contraception.

Male participants must ensure a condom is used for all sexual intercourse as well as following the acceptable methods of contraception listed above for your female partner and ensuring that they are used for the entire duration of the study, and for at least 90 days after you complete this study.

Although pregnancy and lactation are not considered adverse events, it is the responsibility of investigators or their designees to report any pregnancy or lactation in a subject (spontaneously reported to them) that occurs during the trial.

7.2.3 Immediate Reporting of Adverse Events

7.2.3.1 Serious Adverse Events

A serious adverse event is any adverse event occurring at any therapeutic regimen or during any use of the product that:

- Results in death;
- Is life threatening;
- Results in persistent or significant disability/incapacity;
- Results in or prolongs an existing inpatient hospitalization;
- Is a congenital anomaly/birth defect;
- Is another important medical event.

Note: In addition to the above criteria, adverse events meeting either of the below criteria, although not serious per ICH definition, are reportable in the same timeframe as SAEs to meet certain local requirements. Therefore, these events are considered serious for collection purposes.

- Is a cancer;
- Is associated with an overdose.

Refer to [Table 3](#) for additional details regarding each of the above criteria.

For the time period beginning when the consent form is signed until treatment, any serious adverse event, or follow up to a serious adverse event, including death due to any cause, that occurs to any subject must be reported within 24 hours for weekly days or 72 days over the weekend if it causes the subject to be excluded from the trial, or is the result of a protocol-specified intervention, including but not limited to washout or discontinuation of usual therapy, diet, sham treatment or a procedure. The 24 hours for the site starts when the site becomes aware of the SAE. SAEs not reported will be considered a major protocol deviation.

For the time beginning at treatment allocation through 14 days following cessation of treatment, any serious adverse event, or follow up to a serious adverse event, including death due to any cause, whether or not related to the product, must be reported within 24 hours either by electronic media or paper. Electronic reporting procedures can be found in the EDC data entry guidelines. Paper reporting procedures can be found in the Investigator Trial File Binder (or equivalent).

Additionally, any serious adverse event, considered by an investigator who is a qualified physician to be related to the product that is brought to the attention of the investigator at any time outside of the time specified in the previous paragraph also must be reported immediately.

All subjects with serious adverse events must be followed up for outcome.

7.2.3.2 . Events of Clinical Interest (during the stimulation visit 2 (in the 1h after each stimulation))

1. Agitation – daytime or nighttime
2. Confusion or cognitive impairment - daytime or nighttime

Regarding items #1 and 2 above, agitation, confusion or cognitive impairment should be considered an ECI if in the investigator's opinion an acute worsening from baseline has occurred, or there is an unusual or atypical presentation of symptoms for a given subject.

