2.0 TRIAL DESIGN

2.1 Trial Design

This is a double-blinded, parallel, sham-controlled study in PwMS and with significant disability of the upper limb (UL). Participants are exposed to a 6-week run-in period with standard occupational therapy and then randomized to 6 weeks of tSCS or sham combined with ongoing occupational therapy. After completion of the double-blind period, sham-treatment participants will be offered an additional 6 weeks open-label extension (OLE) where they receive active tSCS combined with occupational therapy. Participants in the original active group will be followed with no additional stimulation or occupational therapy to assess the durability of effects. The duration of the run-in, active treatment and extended follow (6 weeks each) are defined based in the previous results from a similar therapy for SCI.

Specific procedures to be performed during the trial, as well as their prescribed times and associated visit windows, are outlined in the Trial Flow Chart - Section 6.0. Details of each procedure are provided in Section 7.0 – Trial Procedures.

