3.4. Safety endpoints

Safety and Tolerability Objectives:

1. Adverse Events (AEs) and Serious Adverse Events (SAEs):

All adverse events, regardless of severity or relatedness to the intervention, will be collected and documented throughout the study period. This includes both serious and non-serious adverse events. Serious adverse events will be defined according to ICH-GCP guidelines as any event that results in death, is life-threatening, requires inpatient hospitalization or prolongation of existing hospitalization, results in persistent or significant disability/incapacity, or a congenital anomaly/birth defect.

2. Discontinuations and Reasons for Discontinuation:

Participant retention will be assessed by monitoring the number of participants who discontinue the study prior to its completion. The reasons for discontinuation (e.g., adverse events, lack of efficacy, personal decision, protocol deviations) will be recorded systematically.

3. Retention Rate:

The retention rate will be defined as the percentage of participants who complete the study intervention and all study visits relative to the total number of participants initially randomized.

4. Attendance Rate:

The percentage of scheduled intervention sessions that each participant attends will be recorded to assess adherence and tolerability.

Hypothesis: We hypothesize that tSCS will be safe and well tolerated in PwMS, with a low incidence of serious adverse events and a high retention rate.

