5.10 Beginning and End of the Trial

The overall trial begins when the first subject signs the informed consent form. The overall trial ends when the last subject completes the last study-related phone-call or visit, discontinues from the trial, or is lost to follow-up (i.e., the subject is unable to be contacted by the investigator).

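### The 14-day SAE reporting window after treatment has no scheduled contact for sham participants who take up the OLE, and the protocol states the SAE reporting period inconsistently

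*Protocol*

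**What the plan says.** **Reporting rule.** Protocol Section 7.2.3.1 covers SAEs whether or not they are related to the product: "For the time beginning at treatment allocation through 14 days following cessation of treatment, any serious adverse event", to be reported within 24 hours. Outside that period, it asks only for SAEs that the investigator judges related.

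**Schedule.** Section 2.1: "Participants are exposed to a 6-week run-in period with standard occupational therapy and then randomized to 6 weeks of tSCS or sham". Sham participants are then offered six weeks of active tSCS in the OLE. For the other arm, "Participants in the original active group will be followed with no additional stimulation or occupational therapy to assess the durability of effects". The flow chart (Section 6.0) puts the end of the double-blind period at Day 84 (±3) and the last visit, labelled OLE, at Day 126 (±5). A safety assessment is marked at that visit, and there is no later column. The visit text numbers its visits differently ("Visit 13, 14 and 29: end of DBP, onset and end of OLE"), but it too ends with the end of the OLE.

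**End of trial.** Section 5.10: "The overall trial ends when the last subject completes the last study-related phone-call or visit" (or discontinues, or is lost to follow-up). No post-OLE call is scheduled anywhere.

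**Other safety text.** Section 3.4 says that all AEs, serious or not and related or not, "will be collected and documented throughout the study period". Section 7.2.5 (Management and Reporting of Adverse Events) has every SAE reported within 24 hours of awareness, gives no closing date, and places active monitoring at study visits and treatment sessions.

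**The concern.** The protocol defines a 14-day period after treatment in which every SAE counts. Yet for the sham participants who receive active tSCS in the OLE, its own schedule stops on about the day that period begins. With active detection tied to visits and sessions, nothing prompts a site to ask about these two weeks.

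For the original active arm the mismatch runs the other way. The 14-day clause expires about four weeks before their last visit, while two other sections carry on without a limit.

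Safety and tolerability of tSCS is Objective 1 (Section 3.1), and Section 1.0 gives safety as one purpose of the OLE. Any pooled statement about SAEs after a full six-week active course would combine one group followed by schedule for about six weeks with another not followed by schedule at all. A site holding an unrelated SAE late in follow-up would also find two different answers on whether it needs 24-hour reporting.

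**Working it through.** **Inputs.** Three periods of 6 weeks (Section 2.1). End of double-blind period Day 84 ±3 and last visit Day 126 ±5 (Section 6.0). Reporting window of 14 days after cessation (Section 7.2.3.1). 30 participants per arm, drop-out 10% (Section 1.0) or 15% (Section 8.9).

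**1. Reproduce the schedule.** 42 + 42 + 42 = Day 126, which is the flow chart's last visit.

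**2. Sham participants treated in the OLE, nominal days.** Stimulation ends on Day 126. Window closes: 126 + 14 = Day 140. Days after the last scheduled contact: 140 − 126 = 14, the whole window.

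**3. The same with visit windows.** Let E be the end of the double-blind period (81 to 87) and V the last visit (121 to 131). Assume the OLE starts at E and lasts 42 days, so stimulation ends at E + 42, and that the end-of-OLE visit is on or after that day (V ≥ E + 42). Uncovered days = E + 42 + 14 − V.

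| E | Stimulation ends | V | Uncovered days |
|---|---|---|---|
| 81 | 123 | 126 | 11 |
| 81 | 123 | 131 | 6 |
| 84 | 126 | 126 | 14 |
| 84 | 126 | 131 | 9 |
| 87 | 129 | 131 | 12 |

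The range is 6 to 14 days. It is 14 whenever the visit falls on the day of the last session.

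**4. Original active arm.** Stimulation ends on Day 84. Window closes: 84 + 14 = Day 98. Scheduled follow-up after last stimulation: 126 − 84 = 42 days. Part of it after the window closes: 126 − 98 = 28 days. With visit windows this is 121 − (87 + 14) = 20 days to 131 − (81 + 14) = 36 days.

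**5. Number concerned.** At most 30 former sham participants. With the quoted drop-out, 30 × 0.90 = 27 or 30 × 0.85 = 25.5, so about 25 to 27 if all who remain accept the OLE.

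**6. The three rules applied to two example SAEs judged unrelated.**

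| | Active arm, Day 110 | OLE-treated, Day 130 |
|---|---|---|
| Section 7.2.3.1 | All-cause clause has expired; related-only clause does not apply | Report within 24 hours |
| Section 7.2.5 | Report within 24 hours of awareness | Report within 24 hours of awareness |
| Section 3.4 | Collect if within the study period | Collect if within the study period |
| Scheduled contact afterwards | Day 126 visit | None |

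The first event gets different answers from Sections 7.2.3.1 and 7.2.5. The second is reportable under both, but no scheduled contact would bring it to light.

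**The case against.** The strongest reply is that the 14 days are a reporting period, not a promise of observation. The clause stands under immediate reporting, and Section 7.2.5 starts its 24 hours at awareness. A death or hospital admission on Day 130 can reach the site without a visit and would then be reportable. Section 5.10 also allows for a last telephone call. This stands: a reader might infer that SAEs in the window cannot be observed, or that they would all be lost, and the documents do not support that. They support the narrower statement that no contact is scheduled to ascertain them.

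A reader might also infer that active-arm SAEs after Day 98 are captured only if related. That is not so. Section 3.4 still collects them, Section 7.2.5 still requires 24-hour reporting, and safety is assessed at the Day 126 visit. A site that reports every SAE within 24 hours throughout satisfies all three sections, so the texts can be followed together. What remains is that Section 7.2.3.1 taken alone gives a shorter rule than Section 7.2.5.

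Setting a last visit at Day 121 against a window closing on Day 140 would suggest a gap of 19 days. That would need stimulation to continue for five days after the visit that marks its end. If the visit is held on Day 121 as the end of the OLE, stimulation has stopped by then and the gap is at most 14 days.

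Finally, the OLE is optional and not randomised, and related SAEs remain reportable at any time. Both points are correct and limit the weight of the finding. They do not supply the missing contact.

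**Conclusion.** The point holds as a gap in scheduled ascertainment together with an inconsistent reporting period. For sham participants who take up the OLE, none of the 14-day window is covered by a scheduled contact on nominal days, and 6 to 14 of its days are uncovered within the visit windows. Original active participants have about 42 days of scheduled follow-up after their last stimulation. Up to half of those exposed to tSCS (30 of 60, if all sham participants accept and complete the OLE) are in the group without follow-up.

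It would be wrong to infer that the between-arm safety comparison is biased. Ascertainment on Days 42 to 84 follows the same schedule in both arms. The inequality concerns only what can be said about SAEs after an active course ends.

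The conclusion assumes that OLE stimulation runs for the stated six weeks directly after the double-blind period, and that no contact is planned in documents outside the protocol, such as the data-entry guidelines. Sham participants who decline the OLE stop at about Day 84 and are not part of the gap. This is a worthwhile, inexpensive correction rather than a threat to the primary result.

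**What to change.** 1. Add one safety telephone contact for OLE-treated participants at or after 14 days from their last stimulation, as a new flow-chart column, and count it as the last study contact under Section 5.10.
2. Reconcile Section 7.2.3.1 with Sections 3.4 and 7.2.5 so that one all-cause SAE reporting period applies in both arms: from allocation to the later of the last study contact or the end of the protocol's own 14-day window. The existing duty to report related SAEs at any later time can stay.

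The cost is at most 30 telephone calls, one flow-chart column and a short rewording. The downside is that the last contact for the last OLE-treated participant moves about two weeks later.

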7.2.3.3 Protocol-Specific Exceptions to Serious Adverse Event Reporting

7.2.4 Evaluating Adverse Events

An investigator who is a qualified physician will evaluate all adverse events with respect to the elements outlined in [Table 3](#). The investigator's assessment of causality is required for each adverse event. Refer to [Table 3](#) for instructions in evaluating adverse events.

7.2.5 Management and Reporting of Adverse Events

All adverse events (AEs), regardless of their severity or relationship to the investigational product, will be systematically assessed, recorded, and reported as follows:

- **Detection:** Investigators will actively monitor participants for any signs or symptoms of adverse events during study visits and treatment sessions.
- **Assessment:** A qualified physician investigator will assess each AE for severity, seriousness, causality, and expectedness according to protocol guidelines and regulatory standards (ICH-GCP).
- **Reporting:**
 - All serious adverse events (SAEs) must be reported to the sponsor within **24 hours** of awareness via the electronic data capture (EDC) system or by paper form if needed.
 - Non-serious AEs will be documented in the case report forms (CRFs) and summarized during regular safety reviews.
- **Follow-up:** All AEs will be followed until resolution, stabilization, or until an adequate explanation is available.
- **Pregnancy and lactation:** Although not considered AEs, any pregnancy or lactation event during the study must also be reported promptly according to protocol procedures.

These procedures are designed to ensure participant safety and regulatory compliance throughout the study.

Table 3 Evaluating Adverse Events

Maximum Intensity	Mild	awareness of sign or symptom, but easily tolerated (for pediatric trials, awareness of symptom, but easily tolerated)
	Moderate	discomfort enough to cause interference with usual activity (for pediatric trials, definitely acting like something is wrong)
	Severe	incapacitating with inability to work or do usual activity (extremely distressed or unable to do usual activities)
Seriousness	A serious adverse event (SAE) is any adverse event occurring at any Therapeutic regimen or during any use of product that:	
	† Results in death ; or	
	† Is life threatening ; or places the subject, in the view of the investigator, at immediate risk of death from the event as it occurred [Note: This does not include an adverse event that, had it occurred in a more severe form, might have caused death.]; or	
	† Results in a persistent or significant disability/incapacity (substantial disruption of one's ability to conduct normal life functions); or	
	† Results in or prolongs an existing inpatient hospitalization (hospitalization is defined as an inpatient admission, regardless of length of stay, even if the hospitalization is a precautionary measure for continued observation. (Note: Hospitalization for an elective procedure to treat a pre-existing condition that has not worsened is not a serious adverse event. A pre-existing condition is a clinical condition that is diagnosed prior to the use of a Hospital del Mar neurosciences product and is documented in the patient's medical history.); or	
	† Is a congenital anomaly/birth defect (in offspring of subject taking the product regardless of time to diagnosis); or	
	Is a cancer (although not serious per ICH definition, is reportable within 24 hours to meet certain local requirements); or	
	Is associated with an over-treatment (whether accidental or intentional). Any adverse event associated with an over-treatment is considered a serious adverse event for collection purposes. An over-treatment that is not	

	associated with an adverse event is considered a non-serious event of clinical interest and must be reported within 24 hours.
	Other important medical events that may not result in death, not be life threatening, or not require hospitalization may be considered a serious adverse event when, based upon appropriate medical judgment, the event may jeopardize the subject and may require medical or surgical intervention to prevent one of the outcomes listed previously (designated above by a †).
Duration	Record the start and stop dates of the adverse event. If less than 1 day, indicate the appropriate length of time and units
Action Taken	Did the adverse event cause the product to be discontinued?
Relationship to Product	
Did the product cause the adverse event? The determination of the likelihood that the product caused the adverse event will be provided by an investigator who is a qualified physician. The investigator's signed/dated initials on the source document or worksheet that supports the causality noted on the AE form, ensures that a medically qualified assessment of causality was done. This initialed document must be retained for the required regulatory time frame. The criteria below are intended as reference guidelines to assist the investigator in assessing the likelihood of a relationship between the test drug and the adverse event based upon the available information
 
The following components are to be used to assess the relationship between the product and the AE; the greater the correlation with the components and their respective elements (in number and/or intensity), the more likely the product caused the adverse event:

Exposure	Is there evidence that the subject was actually exposed to the product such as: reliable history, acceptable compliance assessment (pill count, diary, etc.), expected pharmacological effect, or measurement of drug/metabolite in bodily specimen?
Time Course	Did the AE follow in a reasonable temporal sequence from administration of the product? Is the time of onset of the AE compatible with a drug-induced effect (applies to trials with investigational medicinal products)?
Likely Cause	Is the AE not reasonably explained by another etiology such as underlying disease, other drug(s)/vaccine(s), or other host or environmental factors

Relationship to the Product (continued)	The following components are to be used to assess the relationship between the product and the AE (continued)	
	Dechallenge	
Was the product discontinued or dose/exposure/frequency reduced?
 
If yes, did the AE resolve or improve?
 
If yes, this is a positive dechallenge. If not, this is a negative dechallenge.
 
(Note: This criterion is not applicable if: (1) the AE resulted in death or permanent disability; (2) the AE resolved/improved despite continuation of the product; (3) the trial is a single-Therapeutic regimen drug trial); or (4) product(s) is/are only used one time.)

	Rechallenge	
Was the subject re-exposed to the product in this trial?
 
If yes, did the AE recur or worsen?
 
If yes, this is a positive rechallenge. If not, this is a negative rechallenge.
 
(Note: This criterion is not applicable if: (1) the initial AE resulted in death or permanent disability, or (2) the trial is a single-Therapeutic regimen drug trial); or (3) product(s) is/are used only one time.)
 
NOTE: IF A RECHALLENGE IS PLANNED FOR AN ADVERSE EVENT WHICH WAS SERIOUS AND WHICH MAY HAVE BEEN CAUSED BY THE PRODUCT, OR IF RE-EXPOSURE TO THE PRODUCT POSES ADDITIONAL POTENTIAL SIGNIFICANT RISK TO THE SUBJECT THEN THE RECHALLENGE MUST BE APPROVED IN ADVANCE BY THE CLINICAL DIRECTOR AND THE INSTITUTIONAL REVIEW BOARD/INDEPENDENT ETHICS COMMITTEE.

	Consistency with Trial Treatment Profile	Is the clinical/pathological presentation of the AE consistent with previous knowledge regarding the product or drug class pharmacology or toxicology?
The assessment of the relationship will be reported on the case report forms /worksheets by an investigator who is a qualified physician according to his/her best clinical judgment, including consideration of the above elements.		
Record one of the following:		Use the following scale of criteria as guidance (not all criteria must be present to be indicative of a

	product relationship).
Yes, there is a reasonable possibility of product relationship.	There is evidence of exposure to the product. The temporal sequence of the AE onset relative to the administration of the product is reasonable. The AE is more likely explained by the product than by another cause.
No, there is not a reasonable possibility of product relationship	Subject did not receive the product OR temporal sequence of the AE onset relative to administration of the product is not reasonable OR the AE is more likely explained by another cause than the product. (Also entered for a subject with over-treatment without an associated AE.)

